ACTG NETWORK COORDINATING CENTER
Social & Scientific Systems, Inc., a DLH Holdings Company
[name]
[name] [name]
[contact]

LETTER OF AMENDMENT #1

DATE: June 22, 2023
TO: ACTG CTU Principal Investigators, CRS Leaders, and CTU/CRS Coordinators
FROM: A5362 Protocol Team
SUBJECT: Letter of Amendment #1 for Protocol A5362, Version 2.0

The following information affects the A5362 study and must be forwarded to your institutional review board (IRB)/ethics committee (EC) as soon as possible for their information and review. This Letter of Amendment (LOA) should be implemented immediately, prior to IRB/EC approval, to eliminate immediate hazard to participants.

The following information also affects the Sample Informed Consent (SIC). A letter informing participants about the contents of this LOA and an addendum to the SIC were provided electronically to sites on 16Jun2023.

Sites should implement the LOA immediately and inform IRB/EC and any other applicable regulatory entities of the LOA. Sites are still required to submit an LOA registration packet to the DAIDS Protocol Registration Office (PRO) at the Regulatory Support Center (RSC). Sites will receive a registration notification for the LOA once the DAIDS PRO verifies that all required LOA registration documents have been received and are complete. An LOA registration notification from the DAIDS PRO is not required prior to implementing the LOA. A copy of the LOA registration notification, along with this letter and any IRB/EC correspondence, should be retained in the site's regulatory file.

In April 2023, the study temporarily closed to screening and accrual due to an unanticipated trend in outcome events, which triggered review by the National Institute of Allergy and Infectious Diseases (NIAID) Therapeutic and Prevention Data and Safety Monitoring Board (DSMB), which met on 01Jun2023 to review all available safety and efficacy data from A5362. The DSMB recommended that A5362 permanently close to accrual because of the high rate of treatment failure and TB recurrence. There were no other safety concerns related to study regimen. The A5362 team, NIAID and DAIDS leadership, and ACTG leadership concur with the following DSMB recommendations for implementation:

- Permanently close A5362 to accrual.

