The following are changes (noted in bold or strikethrough) to A5362, Version 2.0, 08Jul2022, titled A “Phase IIc Trial of Clofazimine- and Rifapentine-Containing Treatment Shortening Regimens in Drug-Susceptible Tuberculosis: The CLO-FAST Study.” These changes will be included in the next version of the A5362 protocol if it is amended at a future date. Changes that have already been made (Clarification Memo #1) have been incorporated in the excerpted text shown below (and are no longer presented in bold or strikethrough).

1. Section SCHEMA, DESIGN

The following information has been added to reference the change in study design due to a DSMB review.

Per the June 1, 2023 DSMB review, and permanent closure of accrual, the follow-up schedules for Arm 1 participants will be revised as follows:

- Participants currently on Arm 1 study treatment should complete the 3-month regimen and then be placed on an additional 3 months of continuation phase rifampicin/isoniazid (RH). Based on the DSMB recommendations, an additional 3 months of treatment is necessary to decrease the likelihood of treatment failure and TB relapse in study participants.
- Participants who have already completed Arm 1 treatment should be seen for a follow-up visit within the next 4 weeks of the date of this LOA, at a scheduled or unscheduled visit, to assess whether further treatment is needed.
- Additional extended follow-up visits for participants in Arm 1 will be added at weeks 30, 38, 60, 91 and 117 unless the participant has already been referred for, or already received, 6 months of SOC through the local TB program. The additional visits at weeks 30, 38, and 60 may be performed by telephone only; these calls are to assess the participant’s TB symptoms and determine if it is clinically indicated that the participant should come in for an in-person visit to assess the need for possible poor treatment response (PPTR) assessments and/or referral to SOC treatment.
- If the site investigator diagnoses TB recurrence at any time during Arm 1 follow up, the participant should be referred to 6 months of SOC treatment by the national TB program. For study purposes, such participants should continue to be followed in the study for outcome determination, unless the participant withdraws consent.

Participants in Arm 2 and Arm C should complete their treatment and follow-up schedule as planned; no additional visits are planned for these groups.

2. Section SCHEMA, DURATION

Arm 1:

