- Up to 117 weeks.
- 65 weeks for participants who are or have been diagnosed with TB treatment failure or recurrence and are or have been referred to six months of local SOC treatment by the national/local TB program.

Arm 2: 65 weeks

Arm C: 65 weeks

3. Section SCHEMA, REGIMEN

The following paragraph has been included to add three months of rifampicin/isoniazid for Arm 1 participants who are currently receiving the experimental 3-month treatment regimen as of 16Jun2023. The treatment regimen for all other participants will remain the same.

Arm 1 participants receiving the experimental 3-month treatment regimen as of 16Jun2023:
rifapentine/isoniazid/pyrazinamide/ethambutol (PHZE) + clofazimine (CFZ) 300 mg once daily for 2 weeks; then PHZE + CFZ 100 mg once daily for 6 weeks; then rifapentine/isoniazid/pyrazinamide (PHZ) + CFZ 100 mg once daily for 5 weeks; then rifampicin/isoniazid (RH) for 13 weeks for a total of 26 weeks of study treatment.

4. Section 1.4, Exploratory Objectives

The following objective has been added to align with the addition of Drug-Susceptibility Testing and Sputum AFB Smear and Culture at weeks 91 and 117:

1.4.8 To explore long term outcomes in Arm 1 participants through 117 weeks after randomization.

5. Section 3.0, STUDY DESIGN

The following update to the Arm 1 regimen and follow-up has been added to the end of the section:

Updates following the DSMB reviews in April and June 2023

Following the DSMB reviews in April and June 2023, and the premature closure to accrual of the study, Arm 1 treatment duration and follow-up was revised for participants who are currently on or have completed Arm 1 study treatment without experiencing treatment failure or TB recurrence, and have not already been referred to six months local SOC treatment. Participants in Arm 1 who have not already been referred to six months local SOC treatment will have follow-up extended through week 117.

6. Section 6.1, Schedule of Evaluations

A new Table 6.1-2 has been inserted for the additional visits and assessments for Arm 1 after week 26. The SOE table for Arm C has been renumbered to Table 6.1-3.

Table 6.1-2: Schedule of Evaluations for Arm 1 Who Have Not Been Referred to Local SOC, Additional Visits and Assessments After Week 26

| Evaluation | Follow-up | | | | | | | | | After Week 65 | |

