##### Unfavorable Outcome

- Absence of cure. A participant will be considered to have absence of bacteriological cure if a sputum sample obtained at or after end of treatment for Arm 1 (week 13), or at or after week 17 for Arm 2 is culture-positive in liquid or solid media for an *Mtb* strain genotypically matched with the initial isolate. A second sputum sample, obtained at least four hours following the first sputum collection (see section 6.2.3 of protocol), is required to confirm absence of bacteriological cure.
- Participants who die from any cause during study treatment or follow-up except from violent or accidental cause (e.g., road traffic accident).

- Participants who had a positive culture for *Mtb* when last seen, whether confirmed by a second sample or not, unless determined to have been re-infected.
- Participants experiencing extension of treatment beyond the nominal level (week 13 for Arm 1 and week 26 for Arm 2) due to clinically inadequate response. These cases should be managed individually in conjunction with and after having notified the A5362 Clinical Management Committee (CMC). Extension of treatment to make up missed doses will not count as unfavorable.

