### 5.1.2 Secondary Estimands

Secondary Objective 2.3.2.1: To compare proportions of participants treated with RPT/CFZ-containing regimens who experience favorable composite efficacy outcome at 65 weeks with Arm 2 (6-month SOC controls)	
Estimand description	Difference in proportion with favorable outcomes 65 weeks after initiation of TB therapy (PHZE+CFZ versus RHZE) among individuals aged $\geq 18$ years and with pulmonary TB without demonstrated isoniazid or rifampicin resistance.
Treatment	13-week Experimental Regimen: rifapentine/isoniazid/pyrazinamide/ethambutol (PHZE) + clofazimine (CFZ)  26-week Standard of Care: rifampicin/isoniazid/pyrazinamide/ethambutol (RHZE) followed by rifampicin/isoniazid (RH)
Target population	Analysis set
Individuals aged $\geq 18$ years with confirmed pulmonary TB without demonstrated isoniazid or rifampicin resistance who initiate TB therapy.	Efficacy set (All participants who are randomized to study treatment and are not late exclusions)
Variables	Outcome measure 3.2.1 A
Favorable outcome 65 weeks after initiation of TB therapy following evidence of cure at treatment completion where favorable outcome is defined by any one of the following:  
 
• Liquid culture negative at 65 weeks after TB therapy initiation
 
• No signs or symptoms of ongoing active TB and unable to produce a sputum specimen at 65 weeks after TB therapy initiation
 
• No signs or symptoms of ongoing active TB and a sputum specimen that is contaminated in two liquid cultures without evidence of TB at 65 weeks after TB therapy initiation
 
 Absence of cure at or after treatment completion is an unfavorable outcome.	Favorable clinical/bacteriologic outcome at the 65 week study visit.
Handling of intercurrent events	Handling of missing data

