The following intercurrent events are relevant to the estimand.  1. Death except from violent or accidental cause (e.g., road traffic accident) Unfavorable outcome ( composite strategy )  2. Violent or accidental death Unevaluable outcome* ( hypothetical strategy )  3. Extension of treatment beyond the nominal duration due to clinically inadequate response Unfavorable outcome ( composite strategy )  4. New TB diagnosis due to a new strain of Mtb Unevaluable outcome* ( hypothetical strategy )	Participants lost to follow-up and culture negative at their last visit meet the definition of "unevaluable" and will be censored at the time of their last follow-up visit  Participants with a positive culture for Mtb when last seen, whether confirmed by a second sample or not, unless determined to have been re-infected will be considered to have an unfavorable outcome and the event time will be the visit when last seen.  Participants with a new TB diagnosis due to a new strain of Mtb will be censored at the time of their last follow-up visit.

5. Pregnancy during treatment resulting in discontinuation of initial therapy Unevaluable outcome* (hypothetical strategy)
 
6. Failure to complete treatment (except for 2 and 5 above) All follow-up through to 65 weeks will be used to determine the variable irrespective of duration of treatment (treatment policy strategy)
 
* See handling of missing data for imputation rules for unevaluable outcomes
	Participants who become pregnant during assigned active treatment and discontinue treatment will be censored at the time of treatment discontinuation.
Population-level summary measure	Analysis approach
Difference in cumulative probability of having a favorable clinical/bacteriologic outcome at 65 weeks after TB therapy initiation.	Difference in cumulative proportion of participants at 65 week visit together with 90% and 95% two-sided confidence intervals. We will use the Kaplan-Meier estimator and Greenwood's estimate for the standard error.

Secondary Objective 2.3.2.1: To compare proportions of participants treated with RPT/CFZ-containing regimens who experience favorable composite efficacy outcome at 65 weeks with Arm 2 (6-month SOC controls)	

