#### **5.1.3.8 Proportion of participants who have a TB relapse (Objective 2.3.2.9; Outcome Measure 3.2.8)**

We will estimate the proportion of participants in Arm 1 and Arm 2 with TB relapse using Kaplan-Meier estimates and 95% confidence intervals at 6 months (Arm 1), 9 months (Arms 1 and 2), and 12 months post-treatment (Arm 1 only) in the start treatment/not late exclusion set. We define the time of relapse as the time from end of treatment until the first sputum sample that is culture

positive in liquid or solid media for an *Mtb* strain that has matching genotype with the baseline isolate. A second positive sputum sample obtained at least 4 hours following the first sputum collection is required to confirm a relapse. If the second sputum sample is negative, this will not be counted as a relapse. If a participant is lost to follow-up without a second sputum sample confirmation of relapse (including contaminated or missing), it will be counted as a relapse.

For monitoring and interim reviews, we will estimate the proportion of participants with a confirmed relapse over time with 95% pointwise confidence bands. In addition, we will estimate the proportion of participants with a suspected TB recurrence or poor treatment response after successful culture conversion, even if relapse/recurrence has yet to be confirmed bacteriologically.

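### SAP v3.0 has no rule for the 13 weeks of RH that LOA #1 added in Arm 1, so definition A, relapse and recurrence count RH recipients as event-free after a 13-week regimen

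*SAP*

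**What the plan says.** **Protocol, LOA #1.** Item 3 (Schema, Regimen) applies to "Arm 1 participants receiving the experimental 3-month treatment regimen as of 16Jun2023". After the 13 experimental weeks they receive more treatment: "then rifampicin/isoniazid (RH) for 13 weeks for a total of 26 weeks of study treatment". Item 1 (Schema, Design) gives the reason: "an additional 3 months of treatment is necessary to decrease the likelihood of treatment failure and TB relapse in study participants".

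**SAP v3.0.** The version history says the plan was aligned with LOA #1. Section 2.1 mentions only the LOA's extended follow-up.

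- In Section 5.1.2, the definition A estimand keeps the original treatment (its Treatment row reads "13-week Experimental Regimen: rifapentine/isoniazid/pyrazinamide/ethambutol (PHZE) + clofazimine (CFZ").
- In Section 3.2.1, definition A makes an extension unfavorable only in this case: "extension of treatment beyond the nominal level (week 13 for Arm 1 and week 26 for Arm 2) due to clinically inadequate response". The intercurrent-event list in 5.1.2 has the same single entry: "Extension of treatment beyond the nominal duration due to clinically inadequate response Unfavorable outcome".
- Sections 3.2.1, 3.2.3.1 and 5.1.3.7 put Arm 1 end of treatment (EOT) at week 13.
- Section 5.1.3.8 starts the relapse clock at end of treatment: "We define the time of relapse as the time from end of treatment until the first sputum sample that is culture" positive for a genotype-matched strain. It reports Arm 1 at 6, 9 and 12 months post-treatment. Section 5.1.3.9 uses the same approach for recurrence.

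None of these sections says how participants given the added RH are handled.

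**The concern.** Accrual closed because of a high rate of treatment failure and recurrence, so how often the 13-week regimen fails is something readers will look for in this trial. Some Arm 1 participants had the length of their treatment doubled in order to make those events less likely. The plan keeps them in the Arm 1 denominator. If they have no event, they count as favorable under definition A and as relapse- or recurrence-free in 5.1.3.8 and 5.1.3.9. The definition A result would then carry a 13-week label that does not describe everyone in it. The relapse result would count time on RH as time off treatment.

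**Working it through.** **1. Treatment length.** SAP 2.1 gives Arm 1 as 2 + 6 + 5 = 13 weeks. LOA #1 adds 13 weeks of RH: 13 + 13 = 26, which reproduces the LOA's stated total.

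**2. Who is affected.** The number is not stated.
- With no missed doses (91 days), a participant on treatment at 16 June 2023 started after 17 March 2023.
- The adequate-treatment definition allows 70 + 49 = 119 days, which moves that date to 17 February 2023.
- The LOA dates the stop: "In April 2023, the study temporarily closed to screening and accrual due to an unanticipated trend in outcome events". No day is given. Taking 1 to 30 April, the affected group comes from about 2 to 6 weeks of accrual at 91 days, or 6 to 10 weeks at 119 days.
- Assuming uniform accrual that began between June 2021 and June 2022, this is about 2% to 22% of Arm 1. I use f = 2% to 20%.

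**3. Scoring under definition A.** RH given to everyone on treatment at a date, on a DSMB recommendation, is not an extension for inadequate response. It is therefore not an event. The treatment-policy entry in 5.1.2 covers failure to complete treatment, not added treatment. RH recipients are scored on their later outcome.

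**4. Relapse clock.** With Arm 1 EOT at week 13, 12 months post-treatment is week 13 + 52 = 65, and for Arm 2 nine months is 26 + 39 = 65. The horizons fit week 13. For RH recipients, weeks 13 to 26 are then on treatment. That is 13 of the 26 weeks in the 6-month horizon.

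**5. Size at week 65.** Let p13 be the event probability after 13 weeks alone and p26 the probability with RH. Both are assumed, since the documents give neither. The Arm 1 estimate is (1 − f) × p13 + f × p26, so the understatement is f × (p13 − p26). Example: f = 10%, p13 = 20%, p26 = 5% gives 0.9 × 20 + 0.1 × 5 = 18.5%, which is 1.5 points low.

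| f | p13 = 20%, p26 = 5% | p13 = 30%, p26 = 5% |
|---|---|---|
| 2% | 0.3 points | 0.5 points |
| 5% | 0.75 | 1.25 |
| 10% | 1.5 | 2.5 |
| 20% | 3.0 | 5.0 |

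If p26 = p13, the understatement is zero.

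**6. Early report.** The data cut is the last participant's week 26 visit, so RH recipients are censored early. I used a weekly Kaplan-Meier calculation with events front-loaded (decaying over a 13-week scale, from week 13 without RH and from week 26 with it) and RH recipients censored at weeks 26 to 34. At f = 10% it gives 1.2 to 1.3 points (p13 = 20%) or 1.7 to 2.1 points (p13 = 30%), against 1.5 and 2.5 with full follow-up.

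**7. Scale.** At the planned 110 in Arm 1, the 95% half-width is 1.96 × √(p(1 − p)/110), or 7.5 points at 20% and 8.6 points at 30%. It is wider if fewer were enrolled.

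**The case against.** The strongest reply is that analysis by randomized arm is a legitimate treatment-policy estimate. Objective 2.3.2.9 speaks of participants on Arm 1 and Arm 2, and the 13-week label stands in the definition A estimand, not in 5.1.3.8 or 5.1.3.9. This stands, and the by-arm estimate should be kept. But the SAP does not declare that strategy for added treatment, and a by-arm estimate that includes RH recipients does not answer what happens after 13 weeks alone.

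Other points also stand in part. Positive cultures from week 13 on still count as absence of cure under definition A. SAP 6.4 already plans a summary of treatment extensions, and coding detail may sit in the Analysis Implementation Plan, which is not available here; the choice of estimand still belongs in the SAP. The effect is small beside the sampling error in step 7.

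A reader might infer more than the documents support:

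- **That RH depended on calendar date alone, so censoring at RH start is non-informative.** Being on treatment at 16 June 2023 also depended on missed doses and on not having stopped or failed.
- **That the net bias favors Arm 1.** LOA #1 adds Arm 1 contacts at weeks 30, 38 and 60, which could raise detection and partly offset the effect. Definition B moves the other way: read literally, it makes every extension unfavorable except to make up missed doses.
- **That the relapse horizon runs to week 78.** This would need EOT at week 26 (26 + 52), which conflicts with the SAP's own week 13 and with its horizons.
- **That the main comparison is compromised.** The primary culture-conversion endpoint ends at week 12, before any RH.

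**Conclusion.** The gap is real and should be closed. SAP v3.0 leaves the RH extension without a rule in definition A, relapse and recurrence. As written, recipients without an event count as successes after week 13. If RH does what LOA #1 says it is for, this mechanism understates Arm 1 failure and relapse for the 13-week regimen.

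The range of about 0.3 to 5 percentage points at week 65 rests wholly on assumed inputs: 2% to 20% of Arm 1 affected, 20% to 30% risk after 13 weeks and 5% with RH. The documents support the mechanism and, through the LOA's stated purpose, its direction. They do not fix its size or the net direction of all LOA changes together. The point concerns secondary estimates, for which no hypothesis test is planned.

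**What to change.** In SAP 5.1.2 (definition A), 5.1.3.8 and 5.1.3.9:

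1. List the DSMB-directed RH as an intercurrent event, and state that Arm 1 EOT for these analyses is week 13.
2. Keep the by-arm estimate with RH recipients included, and label it treatment policy.
3. Beside it, report an estimate for the 13-week regimen.
   - *Definition A:* censor at the first RH dose. Date an event by its first positive sample, even if the confirming sample comes after RH starts.
   - *Relapse and recurrence:* with EOT at week 13, censoring at RH start falls at about time zero and amounts to exclusion. Report the result with and without RH recipients instead. Preferably define the excluded group by randomization date (scheduled week 13 later than 16 June 2023, so randomized after 17 March 2023), so that selection does not depend on adherence or response. Censor any RH recipient randomized earlier at the first RH dose.
4. Report the number who received RH as its own line in the Section 6.4 summary, and do not describe the censoring as non-informative.

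The cost is SAP wording, one extra Kaplan-Meier run per outcome, and slightly wider Arm 1 intervals for the 13-week estimate.

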#### **5.1.3.9 Proportion of Participants who have a TB recurrence (Objective 2.3.2.9; Outcome Measure 3.2.10)**

The analysis for the proportion of participants with a TB recurrence will follow the same approach described in Section 5.1.3.8. We define recurrence in the same way as relapse, except it is not required that the TB strain has matching genotype with the baseline sample.

#### **5.1.3.10 Plasma Pharmacokinetic Parameters for CFZ (Objectives 2.3.2.10 and 2.3.2.11; Outcome Measures 3.2.11)**

[name] and team at Radboudumc, The Netherlands, will conduct this analysis.

The PK parameters of interest (Cmin, Cmax, Tmax, AUC0-24h) for CFZ in Arm 1 and Arm C of the alive/adequate treatment set will be estimated using non-compartmental methods applied to concentrations from intensive PK sampling visits. The AUC will be determined using the trapezoidal rule. Cmin will be the minimum observed concentration after the observed dose. Cmax will be the maximum observed concentration. Tmax is the time at which Cmax occurs.

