## 2 Study Overview

### 2.1 Overview of Study Design

A5362 is an open-label, randomized phase IIc study to evaluate whether a 3-month regimen of rifapentine/isoniazid/pyrazinamide/ethambutol (PHZE) with clofazimine (CFZ) dosed as 100 mg daily with a 2-week 300 mg daily loading dose is superior to the standard of care (SOC) 6-month regimen of rifampin/isoniazid/pyrazinamide/ethambutol (RHZE) for DS-TB with respect to (1) early bacteriologic efficacy defined as time to culture conversion by 12 weeks post-randomization and (2) safety over 65 weeks.

Participants will be randomized to one of three treatment arms; Arm 1 with treatment for 13 weeks (including a 2-week CFZ loading dose of 300 mg daily; Arm 2 with treatment for 26 weeks; or Arm C with treatment for 4 weeks with an experimental regimen and the remaining 22 weeks with SOC (PK subgroup)).

- Arm 1 (Experimental): PHZE + CFZ 300 mg once daily for 2 weeks, PHZE + CFZ 100 mg once daily for 6 weeks; then PHZ + CFZ 100 mg once daily for 5 weeks
- Arm 2 (SOC): RHZE for 8 weeks; then RH for 18 weeks
- Arm C (PK subgroup): PHZE + CFZ 100 mg once daily for 4 weeks; then on study, off study medications and treated according to SOC (RHZE for 4 weeks; RH for 18 weeks)

We will follow all participants in Arms 1, 2, and C from randomization to week 65 for the primary and secondary objectives. Protocol v2.0 LOA #1 also includes extended follow-up for some participants corresponding to new exploratory objectives which will be detailed in a separate SAP.

Participants who consent to intensive PK sampling visits will be randomized to Arms 1, 2, or C in a 2:1:1 ratio, respectively, while participants who do not consent to intensive PK sampling will be

randomized only to Arms 1 or 2 in a 2:1 ratio, respectively. We will stratify randomization based on HIV status and the presence of advanced disease as determined by chest X-ray. We will balance randomization by institution.

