#### Definitions of Adequate Treatment Within 3-month Regimen (Arm 1)

- Taken a total of at least 56 doses of allocated intensive phase treatment within 70 days of starting treatment
- AND taken at least 28 doses of continuation phase treatment within 49 days (7 weeks) of completion of the intensive phase
- AND missed no more than 21 doses of medication overall.

Definitions of Adequate Treatment within 6-month Regimen (Arm 2)

- Taken a total of at least 56 doses of allocated intensive phase treatment within 70 days of starting treatment
- AND taken at least 100 doses of continuation phase treatment within 154 days (22 weeks) of completion of the intensive phase
- AND missed no more than 42 doses of medication overall.

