We will report the minimum concentration (Cmin), maximum concentration (Cmax), time of Cmax (Tmax), and area under the concentration curve (AUC0-24h) estimated through non-compartmental analysis for weeks 2 and 13 summarized separately.

Arm C

We will report the estimated minimum concentration (Cmin), maximum concentration (Cmax), time of Cmax (Tmax), and area under the concentration curve (AUC0-24h) estimated through non-compartmental analysis for week 2.

Arm 1 versus Arm C

We will compare the estimated minimum concentration (Cmin), maximum concentration (Cmax), time of Cmax (Tmax), and area under the concentration curve (AUC0-24h) at week 2 between Arm 1 and Arm C intensive PK participants. We will estimate the geometric mean ratio comparing Arm 1 to Arm C and corresponding 90% confidence interval. As a supplemental analysis, we will use a Wilcoxon rank sum test and report the p-value.

3.2.12 Change from baseline in skin pigmentation (colorimetric L\*, a\*, b\* parameters) utilizing ambient light-independent reflectance mapping at weeks 8, 13, 26, and 65.

Mean change in total color difference from week 0 to each of weeks 8, 13, 26, 65 in Arm 1 vs Arm 2 at each of the following locations; (1) left cheek, (2) right cheek, (3) forehead, (4) chin.

Mean change in total color difference from week 0 to each of weeks 8, 13, 26, 65 in Arm 1 vs Arm 2 using, for each participant, the location with the maximum change.

3.2.13 Change from baseline in participant-reported changes in skin pigment and distress related to perceived skin hyperpigmentation at weeks 8, 13, 26, and 65.

Mean subjective 'change in coloration' score between week 0 and weeks 8, 13, 26, and 65 in Arm 1 vs Arm 2 (10-point numeric rating scale where 0=none, 10=most significant possible).

Mean subjective 'distress related to skin coloration' score at each of weeks 0, 8, 13, 26, and 65 in Arm 1 vs Arm 2 (10-point numeric rating scale where 0=none, 10=worst possible)

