#### 4.1.1 Analysis set definitions

##### 4.1.1.1 Analysis sets (used for primary (5.1.1) and key secondary (5.1.2) estimands):

- **Efficacy Set:**  
All participants who are randomized to study treatment and are not late exclusions.  
(Participants will be late exclusions if they do not have any positive culture (liquid or solid) at screening, entry, or week 1, or if they have TB that is RIF-resistant or INH-resistant identified at screening or entry.)
- **Safety Set:**  
All participants who start assigned study treatment.
- **Start treatment/not late exclusion set:**  
All participants who start assigned study treatment and are not late exclusions.
- **Alive/adequate treatment set:**  
All participants who complete an adequate course of treatment as defined within Sections 10.2.5 and 10.2.6 of the protocol and who do not die during treatment.
- **Per protocol Set:**  
All participants who start and complete assigned study treatment.

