##### Arm 1 versus Arm C

We will estimate the geometric mean ratio for each PK parameter (Cmin, Cmax, Tmax, AUC0-24h) together with the 90% confidence interval using available data in the alive/adequate treatment set.

This non-compartmental analysis will be in conjunction with non-linear mixed-effects modeling to estimate the primary PK parameters (e.g., apparent oral clearance (CL/F), volume of distribution, rate of absorption). The model-based analysis will use the intensive PK samples as well as the sparse samples collected throughout the study period and all protein concentration data. We will model the PK observations continuously over time, taking in account each participant's actual dosing history. We will conduct a covariate analysis to evaluate the potential impact of demographics and concomitant medications. We will compare the derived secondary metrics with the non-compartmental analysis results in a posterior predictive check.

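### SAP 5.1.3.10 admits week 2 clofazimine profiles to the Arm 1 versus Arm C ratio only if the participant later completes adequate treatment and survives it, a condition absent from SAP 3.2.11

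*SAP*

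**What the plan says.** SAP 5.1.3.10 obtains Cmin, Cmax, Tmax and AUC0-24h by non-compartmental methods "for CFZ in Arm 1 and Arm C of the alive/adequate treatment set". Under its Arm 1 versus Arm C heading, the geometric mean ratio and 90% confidence interval are computed "using available data in the alive/adequate treatment set". The restriction is thus stated twice.

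SAP 4.1.1.1 defines the set as "All participants who complete an adequate course of treatment as defined within Sections 10.2.5 and 10.2.6 of the protocol", and further requires that they do not die during treatment. For Arm 1, SAP 3.2.1 gives three conditions for adequate treatment:

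- The intensive-phase condition reads: "Taken a total of at least 56 doses of allocated intensive phase treatment within 70 days of starting treatment".
- The second condition asks for 28 or more continuation doses, all inside the 49 days that follow the intensive phase.
- The third caps missed doses at 21 over the whole course.

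The SAP gives a parallel rule for the 6-month regimen, labelled Arm 2. Neither rule is labelled for Arm C.

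SAP 3.2.11 describes the same contrast as a comparison "at week 2 between Arm 1 and Arm C intensive PK participants" and mentions neither completion nor survival. Arm C has non-compartmental parameters at week 2 only; Arm 1 has them at weeks 2 and 13. On allocation, SAP 2.1 states: "Participants who consent to intensive PK sampling visits will be randomized to Arms 1, 2, or C in a 2:1:1 ratio".

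**The concern.** Objective 2.3.2.11 asks how CFZ exposure differs with and without a loading dose, and the comparison is made at week 2. The natural population is everyone randomised among the PK consenters to Arm 1 or Arm C who has a usable profile at that visit. The set in 5.1.3.10 instead depends on what happens well after the sample is drawn. An Arm 1 participant dosed as planned to week 2, with a complete profile, drops out of the ratio if they stop treatment in week 9 or die in week 10. SAP 5.1.3.1 uses failure of the same adequacy rule as its tolerability outcome, so the PK comparison is conditioned on another endpoint of the trial.

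Three things are at stake: loss of profiles from a small subgroup, loss of the protection that randomisation gives the loading-dose comparison, and uncertainty about which population the reported ratio describes.

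**Working it through.** **No plan figure to reproduce.** SAP 2.4 gives sample size and power for the primary outcomes only. There is no stated power, variability or expected ratio for the PK comparison.

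**When Arm 1 membership is settled.** Inputs from SAP 3.2.1: at least 56 intensive-phase doses within 70 days, then at least 28 continuation doses within 49 days. Assumptions: one dose per day, and week 2 sampling on about day 14.

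- Earliest the rule can be met: 56 + 28 = 84 doses, so day 84.
- Gap after the week 2 profile: 84 − 14 = 70 days.
- Latest permitted: 70 + 49 = day 119.
- Scheduled Arm 1 treatment is 13 weeks, or 91 days, of which 91 − 14 = 77 fall after week 2.

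These figures show timing only. They are not exclusion rates.

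**The two descriptions side by side.**

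| | SAP 3.2.11 | SAP 5.1.3.10 with 4.1.1.1 |
|---|---|---|
| Contrast | Arm 1 versus Arm C, week 2 | Arm 1 versus Arm C geometric mean ratio |
| Who | Intensive PK participants | Alive/adequate treatment set |
| Later completion required | Not stated | Yes |
| Survival through treatment required | Not stated | Yes |
| Rule for Arm C | Not needed | By reference to protocol 10.2.5 and 10.2.6; SAP text labels Arms 1 and 2 only |

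**Planned size.** About 20 in Arm C (SAP 2.4) and 2:1:1 allocation (SAP 2.1) imply about 2 × 20 = 40 PK participants in Arm 1, so 60 planned profiles. Accrual closed early and the actual PK numbers are not given.

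**Precision.** On the log scale the 90% half-width is z × s × √(1/n1 + 1/nC). If both arms lose the same fraction f, each n becomes n(1 − f), and the width grows by the factor 1/√(1 − f) whatever the starting sizes. The documents give no exclusion rate, so f is assumed.

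| f (assumed) | Profiles lost of 60 | 1/√(1 − f) | Wider by | Wider by, t quantiles from 40/20 |
|---|---|---|---|---|
| 5% | 3 | 1.026 | 2.6% | 2.7% (38/19) |
| 10% | 6 | 1.054 | 5.4% | 5.6% (36/18) |
| 20% | 12 | 1.118 | 11.8% | 12.3% (32/16) |

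**Bias.** Let excluded participants have g times the geometric mean of those included, with the same g in both arms, and let e1 and eC be the excluded fractions. Then the restricted ratio divided by the full ratio is g^(eC − e1). It equals 1 when the fractions are equal, and otherwise moves up or down depending on g and on which arm loses more. The documents give none of these inputs, so no bias figure is claimed.

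**The case against.** **The two sections do not contradict each other.** SAP 4.1 says that the analysis set is specified with the analysis of each objective. Section 3 defines measures and Section 5 assigns populations, as happens for tolerability and skin colour. On that view, 3.2.11 identifies who has intensive profiles and 5.1.3.10 narrows them to the overlap. This stands: a reader might infer a direct conflict, but the documents support only that the sections are unreconciled. It does not supply a reason for conditioning a week 2 comparison on later completion.

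**Adherence matters for PK.** It does, but the relevant dosing is that before the profile. A reader might go further and say that the set also lets in badly dosed profiles, because the adequacy rule tolerates early missed doses. The documents do not show that such a profile would be taken or analysed; any dosing conditions for the PK visits may sit in protocol sections not supplied.

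**The mixed-effects model mitigates the loss.** SAP 5.1.3.10 says that this model uses the intensive and sparse samples, allows for actual dosing history, and names no restricted set. It is unaffected, so excluded profiles are not lost to the PK evaluation as a whole. They remain outside the reported ratio.

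**Arm C may be covered in the protocol.** A reader might infer that no adequacy rule exists for Arm C. That cannot be concluded: the set is defined by protocol 10.2.5 and 10.2.6, and the supplied protocol document is a letter of amendment without those sections.

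**The effect is unproven and probably modest.** This is fair. Every exclusion rate above is assumed, and even 10% in both arms costs only about 5% in interval width.

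**Conclusion.** The point holds in a limited form. Followed as written, SAP 5.1.3.10 removes valid week 2 profiles from a randomised comparison because of post-randomisation events that, in Arm 1, cannot be fully resolved until at least day 84. SAP 3.2.11 does not carry that condition, and how Arm C participants qualify is not clear from the SAP.

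The day 84 figure rests on one dose per day. The cost in precision, 2.6% to 11.8% in interval width, rests on assumed equal exclusion of 5% to 20% in both arms.

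Two stronger conclusions are not supported. One is that the ratio is biased: the documents give neither exclusion rates nor exposures of those excluded, and the bias may be negligible. The other is that the Arm 1 week 13 summary is also at fault: week 13 is the nominal end of Arm 1 treatment, so completion and sampling largely coincide, and no harm is shown there.

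The change should be made, at low-to-moderate priority. Under SAP 2.3 the only formal superiority test is for the primary efficacy objective; this secondary objective is reported by estimates and intervals.

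**What to change.** - For the week 2 summaries and the Arm 1 versus Arm C ratio, use all Arm 1 and Arm C intensive PK participants with an evaluable week 2 profile and documented CFZ dosing before it, irrespective of later treatment completion or survival.
- Define this PK set in SAP 4.1.1.1, stating what makes a profile evaluable and what dosing record is required. Both criteria should depend only on information up to the week 2 visit.
- Name the same set in SAP 3.2.11 and 5.1.3.10.
- Keep the alive/adequate treatment set at most as a sensitivity analysis, and state how Arm C participants enter it after checking protocol 10.2.5 and 10.2.6.

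The Arm 1 week 13 summary and the mixed-effects model need no change on this account. The cost is SAP wording and minor analysis work, with no new visits or samples.
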